## **Study Summary**

Coagulopathy of COVID-19 afflicts approximately 20% of patients with severe COVID-19 and is associated with need for critical care and death. COVID-19 coagulopathy is characterized by elevated D-dimer, an indicator of fibrin formation and clot lysis, and a mildly prolonged prothrombin time, suggestive of coagulation consumption. To date, it seems that COVID-19 coagulopathy manifests with thromboembolism, thus anticoagulation may be of benefit. We propose to conduct a parallel pragmatic multi-centre open-label randomized controlled trial to determine the effect of therapeutic anticoagulation compared to standard care in hospitalized patients admitted for COVID-19 with an elevated D-dimer.

**Current Protocol Version:** Version 1.4 – 13 Oct 2020

**Clinical trial registration:** <https://clinicaltrials.gov/ct2/show/NCT04362085>

**GCP Statement**

This study document is the protocol for research involving human participants. This study is to be conducted according to Canadian and international standards, and in compliance with the protocol, International Conference on Harmonisation Good Clinical Practice E6 (ICH-GCP), World Medical Association Declaration of Helsinki: Ethical Principles for Medical Research Involving Human Participants, and all applicable regulatory and institutional requirements and research policies.

## Protocol Synopsis

Full Title	Coagulopathy of COVID-19: A Pragmatic Randomized Controlled Trial of Therapeutic Anticoagulation versus Standard Care as a Rapid Response to the COVID-19 Pandemic
Short Title	RAPID COVID COAG
Version Number and Date	Version 1.4, 13 Oct 2020
Clinical Phase	III
Study Duration	
Enrollment period: April 24, 2020 to March 10, 2022
 
Study period: April 24, 2020 to April 24, 2022

Co-Principal Investigators	[name], [name] [name] and [name]
Study Design	Open-label, parallel, 2-arm randomized controlled trial
Primary Objective	To determine the effect of therapeutic anticoagulation, with low molecular weight heparin or unfractionated heparin (high dose nomogram), compared to standard care in hospitalized patients admitted for COVID-19 with an elevated D-dimer on the composite outcome of intensive care unit (ICU) admission, non-invasive positive pressure ventilation, invasive mechanical ventilation or death at 28 days.
Secondary Objectives	
To compare the following secondary outcomes between study arms up to day 28:
 
 
1. All-cause death;
 
2. Composite of ICU admission or all-cause death;
 
3. Composite of mechanical ventilation or all-cause death;
 
4. Major bleeding as defined by the ISTH Scientific and Standardization Committee (ISTH-SSC) recommendation;
 
5. Red blood cell transfusion (<math>\geq 1</math> unit);
 
6. Transfusion of platelets, frozen plasma, prothrombin complex concentrate, cryoprecipitate and/or fibrinogen concentrate;
 
7. Renal replacement therapy;
 
8. Hospital-free days alive;
 
9. ICU-free days alive;
 
10. Ventilator-free days alive;
 

	
 
11. Organ support-free days alive;
 
12. Venous thromboembolism (defined as symptomatic or incidental, suspected or confirmed via diagnostic imaging and/or electrocardiogram where appropriate);
 
13. Arterial thromboembolism (defined as suspected or confirmed via diagnostic imaging and/or electrocardiogram where appropriate);
 
14. Heparin induced thrombocytopenia;
 
15. Trajectories of COVID-19 disease-related biomarkers.
 

Sample Size	462 patients (231 per group).
Randomization	1:1 randomization, centralized web-based randomization.
Study Population	The study population includes hospitalized adults admitted for COVID-19 prior to the development of critical illness. We have excluded individuals where the bleeding risk or risk of transfusion would generally be considered unacceptable, those already therapeutically anticoagulated and those who would have already met components of our primary outcome.
Investigational Product Description	Therapeutic dose low molecular weight heparin (Dalteparin, Enoxaparin, Tinzaparin) or high dose nomogram of unfractionated heparin.
Control	Standard care (thromboprophylactic doses of low molecular weight heparin (Dalteparin, Enoxaparin, Tinzaparin, Fondaparinux) or unfractionated heparin.
Duration of Treatment	Therapeutic anticoagulation will be administered until discharged from hospital, 28 days or death. If the patient is admitted to the ICU or requiring ventilatory support, we recommend continuation of the allocated treatment as long as the treating physician is in agreement.
Outcome Measures	Primary: composite outcome of intensive care unit (ICU) admission, non-invasive positive pressure ventilation, invasive mechanical ventilation or death at 28 days.
	
Secondary (evaluated up to day 28):
 
 
1. All-cause death
 
2. Composite of ICU admission or all-cause death
 
3. Composite of mechanical ventilation or all-cause death
 

	
 
4. Major bleeding as defined by the ISTH Scientific and Standardization Committee (ISTH-SSC) recommendation;
 
5. Red blood cell transfusion (<math>\geq 1</math> unit);
 
6. Transfusion of platelets, frozen plasma, prothrombin complex concentrate, cryoprecipitate and/or fibrinogen concentrate;
 
7. Renal replacement therapy;
 
8. Hospital-free days alive;
 
9. ICU-free days alive;
 
10. Ventilator-free days alive;
 
11. Organ support-free days alive;
 
12. Venous thromboembolism (defined as symptomatic or incidental, suspected or confirmed via diagnostic imaging and/or electrocardiogram where appropriate);
 
13. Arterial thromboembolism (defined as suspected or confirmed via diagnostic imaging and/or electrocardiogram where appropriate);
 
14. Heparin induced thrombocytopenia;
 
15. Trajectories of COVID-19 disease-related biomarkers.
 

Statistical Analysis	
Primary analyses will be by in the intention-to-treat population of all randomized patients in accordance with the originally allocated intervention. We will conduct a chi-square test for the main analysis of the primary outcome and use a generalized linear regression model with binary distribution and identity link to derive risk difference with 95% confidence intervals.

## 1.0 Background

Coagulopathy of COVID-19 appears to afflict approximately 20% of patients with severe COVID-19 and is associated with need for critical care and death (1–3). COVID-19 coagulopathy is characterized by elevated D-dimer, an indicator of fibrin formation and clot lysis, and a mildly prolonged prothrombin time (PT), suggestive of coagulation consumption (2–6). In the largest study to date, Guan et al. described 560 patients with COVID-19 where D-dimer was measured and was elevated D-dimer ( $\geq 0.5$  mg/L) in 60% of those with severe illness (1,4). In fact, Zhou et al. noted that a D-dimer concentration greater than 1  $\mu$ g/mL was associated with mortality in 191 patients with COVID-19 (odds ratio [OR] 18.42, 95%CI: 2.64-128.55,  $p = 0.0033$ ) (5). In a study by Tang et al., where they specifically examined laboratory coagulation parameters in 183 patients, they found that non-survivors of COVID-19 had a D-dimer of 2.12 $\mu$ g/mL (range: 0.77-5.27 $\mu$ g/mL) compared to survivors with 0.61 $\mu$ g/mL (range: 0.61-1.29  $\mu$ g/mL) (3). Low fibrinogen has been more rarely described with severe COVID-19 and seems to occur later in the course of hospitalization (3). Interestingly, thrombocytopenia, typically associated with sepsis mortality, is not a consistent manifestation of COVID-19 coagulopathy and does not appear to correlate with severity of illness. In fact, very few patients have clinically relevant thrombocytopenia (i.e. a platelet count below  $50 \times 10^9/L$ ) (6,7).

In the published literature thus far, it seems that COVID-19 coagulopathy may manifest with thrombosis of the pulmonary microvasculature with secondary pulmonary hemorrhagic infarction and necrosis(2,8). Moreover, there are numerous animal models of acute lung injury describing the benefit of anticoagulation (9,10). Tang et al. found that in patients with severe COVID-19 and laboratory evidence of early disseminated intravascular coagulation (DIC), using the sepsis-induced coagulopathy (SIC) score, had a lower risk of death when treated with low molecular weight heparin (LMWH) or unfractionated heparin (UFH) at thromboprophylactic doses for 7 days or longer (2). In fact, the authors found that 28-day mortality of heparin users were lower than non-users in patients with SIC scores  $\geq 4$  (40.0% vs. 64.2%,  $p = 0.029$ ), or D-dimer  $> 6$  times the upper limit of normal (ULN) (32.8% vs. 52.4%,  $p=0.017$ )(2). However, this study was limited by its retrospective nature and did not account for other treatments that were provided. Moreover, a recent study by Klok et al. of 184 critically ill patients with COVID-19, reported a 31% incidence of arterial and venous thromboembolism despite pharmacological thromboprophylaxis (11). To the best of our knowledge, there have been very few published reports of clinically significant hemorrhage as a clinical manifestation of COVID-19 coagulopathy (12). Thus, anticoagulation with heparin-based therapy, whether unfractionated or low molecular weight (Dalteparin, Enoxaparin, Tinzaparin), for severe COVID-19 may theoretically be of benefit (9,10).

Currently, our group is conducting a systematic review and meta-analysis to describe hemostatic parameters and relevant clinical outcomes (e.g. thromboembolism, bleeding, death) among patients with COVID-19 (PROSPERO: (13)). To date, there are 62 full-text articles that have met our inclusion criteria and data extraction is ongoing.

COVID-19 coagulopathy is such an increasingly recognized manifestation of severe illness, that the International Society on Thrombosis and Haemostasis (ISTH) recently published a guidance document on its management despite the current paucity of evidence (4). In addition, anticoagulation for patients with severe COVID-19 has been recommended by a Chinese expert consensus statement, however without proper evidence to support its efficacy (14). Moreover, there is evidence that D-dimer levels and markers of inflammation vary at baseline according to race/ethnicity with more adverse levels in Hispanic and especially African-American persons (15,16). This, combined with the observation that individuals of minority groups are more likely to experience severe and fatal COVID-19 highlights the need to evaluate whether the effect of anticoagulation, and COVID-19 coagulopathy biomarkers differ by race/ethnicity.

We believe that the current knowledge of COVID-19 coagulopathy provides rationale for a pragmatic randomized controlled trial (RCT) to evaluate the effectiveness of therapeutic anticoagulation with LMWH or UFH (high dose nomogram) in patients with severe COVID-19 and an elevated D-dimer compared to standard care, which typically includes LMWH or UFH at thromboprophylactic doses.

## 2.0 Objectives

### Primary objective:

To determine the effect of therapeutic anticoagulation, with LMWH or UFH (high dose nomogram), compared to standard care in hospitalized patients admitted for COVID-19 with an elevated D-dimer on the composite outcome of intensive care unit (ICU) admission, non-invasive positive pressure ventilation, invasive mechanical ventilation or death at 28 days.

### Secondary objectives:

To determine the effect of therapeutic anticoagulation, with LMWH or UFH (high dose nomogram), compared to standard care in hospitalized patients admitted for COVID-19 with an elevated D-dimer, up to day 28, on:

1. All-cause death;
2. Composite of ICU admission or all-cause death;
3. Composite of mechanical ventilation or all-cause death;
4. Major bleeding as defined by the ISTH Scientific and Standardization Committee (ISTH-SSC) recommendation;
5. Red blood cell transfusion ( $>1$  unit);
6. Transfusion of platelets, frozen plasma, prothrombin complex concentrate, cryoprecipitate and/or fibrinogen concentrate;
7. Renal replacement therapy defined as continuous renal replacement therapy {CRRT} or intermittent hemodialysis {IHD};
8. Hospital-free days alive;
9. ICU-free days alive;
10. Ventilator-free days alive;
11. Organ support-free days alive (see Appendix 4 for definition);
12. Venous thromboembolism (defined as symptomatic or incidental, suspected or confirmed via diagnostic imaging and/or electrocardiogram where appropriate recognizing that access to diagnostic imaging may be limited in the midst of the COVID-19 pandemic. Confirmatory testing at a later date once exposure risk/personal protective utilization is not an issue is encouraged);
13. Arterial thromboembolism (defined as suspected or confirmed via diagnostic imaging and/or electrocardiogram where appropriate recognizing that access to diagnostic imaging may be limited in the midst of the COVID-19 pandemic. Confirmatory testing at a later date once exposure risk/personal protective utilization is not an issue is encouraged);
14. Heparin induced thrombocytopenia;
15. Trajectories of COVID-19 disease-related biomarkers.

[figure not shown]
### Tertiary Objective

16. To explore whether the above outcomes differ by age, sex, diabetes mellitus, coronary artery disease, hypertension, race/ethnicity, D-dimer levels and hypoxia.

The use of BIPAP or CPAP at night or when sleeping for sleep apnea is not considered non-invasive mechanical ventilation or organ support for the purpose of this trial.

### 3.0 Study Design

We propose to conduct a 2-arm, parallel, pragmatic, multi-centre, open-label randomized controlled trial to determine the effect of therapeutic anticoagulation on the composite outcome of ICU admission, invasive mechanical ventilation or death in hospitalized patients admitted for COVID-19. Eligible participants will be randomized to one of two treatment regimens, receiving either therapeutic anticoagulation or standard care until discharged from hospital, death or day 28. If the patient is admitted to the ICU or requiring ventilatory support, we recommend continuation of the allocated treatment as long as the treating physician is in agreement. Randomization will be stratified by site and age (>65 versus ≤65 years) using a 1:1 computer-generated random allocation sequence with variable block sizes. Randomization will occur within the first 5 days (i.e. 120 hours) of participant hospital admission. However, it is recommended that randomization occurs as early as possible after hospital admission. Central randomization using an interactive web response system will ensure allocation concealment. This is an open label study. Blinding of participants, clinical research staff, and clinicians is not possible due to the nature of the intervention. However, the biostatisticians will be blinded at the data analysis phase. Given the objective nature of the primary outcome and the need for pragmatic approaches for this rapid response trial, an independent, blind clinical events committee is not planned (17). See Figure 1 for study schematic.

**Figure 1. RAPID COVID-COAG Study Schematic**

Administer until hospital discharge, death or day 28, if the patient is admitted to the ICU or requiring ventilatory support, we recommend continuation of the allocated treatment as long as the treating physician is in agreement;

For participants treated with UFH: aPTT or UFH anti-Xa will be drawn according to local institutional UFH nomogram protocol guidance;

a single D-dimer test (if not collected through standard of care) on day 2 after randomization (+/- 24 hours) will be collected for participants in both study arms (considering the day of randomization as day 1).

All laboratory results, when available, will be collected from standard of care from admission to hospital discharge, death or 28 days from patient chart

## 4.0 Study Population

The study population includes hospitalized adults admitted for COVID-19 prior to the development of critical illness. We have excluded individuals where the bleeding risk or risk of transfusion would generally be considered unacceptable, those already therapeutically anticoagulated and those who would have already met components of our primary outcome. Participants are recruited from hospital sites in Argentina, Brazil, Canada, Ireland, Saudi Arabia, United Arab Emirates, and the United States of America.

The inclusion criteria are:

- 1) Laboratory confirmed COVID-19 (diagnosis of SARS-CoV-2 via reverse transcriptase polymerase chain reaction as per the World Health Organization protocol or by nucleic acid based isothermal amplification). Positive test prior to hospital admission **OR** within first 5 days (i.e. 120 hours) after hospital admission;
- 2) Admitted to hospital for COVID-19;
- 3) One D-dimer value above ULN (within 5 days (i.e. 120 hours) of hospital admission) **AND EITHER:**
  - a. D-Dimer  $\geq$ 2 times ULN **OR**
  - b. D-Dimer above ULN and Oxygen saturation  $\leq$  93% on room air;
- 4)  $\geq$  18 years of age;
- 5) Informed consent from the patient (or legally authorized substitute decision maker).

The exclusion criteria are:

- 1) pregnancy;
- 2) hemoglobin  $<80$  g/L in the last 72 hours;
- 3) platelet count  $<50 \times 10^9$ /L in the last 72 hours;
- 4) known fibrinogen  $<1.5$  g/L (if testing deemed clinically indicated by the treating physician prior to the initiation of anticoagulation);
- 5) known INR  $>1.8$  (if testing deemed clinically indicated by the treating physician prior to the initiation of anticoagulation);
- 6) patient already on intermediate dosing of LMWH that cannot be changed (determination of what constitutes an intermediate dose is to be at the discretion of the treating clinician taking the local institutional thromboprophylaxis protocol for high risk patients into consideration);
- 7) patient already on therapeutic anticoagulation at the time of screening (low or high dose nomogram UFH, LMWH, warfarin, direct oral anticoagulant (any dose of dabigatran, apixaban, rivaroxaban, edoxaban);
- 8) patient on dual antiplatelet therapy, when one of the agents cannot be stopped safely;
- 9) known bleeding within the last 30 days requiring emergency room presentation or hospitalization;
- 10) known history of a bleeding disorder of an inherited or active acquired bleeding disorder;
- 11) known history of heparin-induced thrombocytopenia;
- 12) known allergy to UFH or LMWH;
- 13) admitted to the intensive care unit at the time of screening;
- 14) treated with non-invasive positive pressure ventilation or invasive mechanical ventilation at the time of screening (of note: high flow oxygen delivery via nasal cannula is acceptable and is not an exclusion criterion);
- 15) Imminent death according to the judgement of the most responsible physician;

- 16) enrollment in another clinical trial of antithrombotic therapy involving pre-intensive care unit hospitalized patients.

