**High Flow Nasal Cannula:**

**For the purposes of this trial, a patient is considered to be receiving high flow nasal cannula (HFNC) therapy when the flow rates provided by this device are >30 L/min.**

For HFNC therapy, the FiO2 and flow rate are independent settings.

Thus, you cannot infer the FiO2 based on the flow rate.

The user controls both and thus should simply enter the FiO2 that was set for the patient.

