## Appendix 4. Outcome Definition for Organ-support Free Days

### Outcome Definition for Organ-support Free Days

Defined as the number of days that a patient is alive and free of organ support through 28 days after trial entry. Organ support is defined as receipt of non-invasive mechanical ventilation, high flow nasal cannula oxygen, invasive mechanical ventilation, or vasopressor therapy.

- Non-invasive mechanical ventilation is defined as BIPAP or CPAP when used for acute respiratory support (the use of BIPAP or CPAP at night or when sleeping for sleep apnea is not considered organ support).
- High Flow Nasal Cannula Oxygen is defined as receiving  $\geq 30$  l/min flow at  $\text{FiO}_2 \geq 40\%$ .
- Invasive mechanical ventilation is defined as positive pressure ventilation through endotracheal tube or tracheostomy.
- Vasopressor support includes infusion of any vasoactive or inotropic medication.
- A patient must be extubated and not receiving mechanical ventilation for at least 2 days before being considered free of mechanical ventilation. If a patient was extubated and re-intubated and placed back on mechanical ventilation within 1 or 2 days, the patient is considered to be on mechanical ventilation during those 1 or 2 days before re-intubation.
- Any patient dying in the acute hospital stay are assigned 28 Day Organ-Support Free Days of -1.
- If there is intervening time in which a patient is free of organ support but goes back on organ support the intervening time does not count toward the organ support free days endpoint. Only time before organ support and after the last use of organ support are counted as "free days."
- If a patient was discharged alive without mechanical ventilation prior to Day 28, the patient is assumed to be free of organ support after hospital discharge for the remainder of the 28 days.
- If a patient was discharged alive on mechanical ventilation (invasive or non-invasive) prior to day 28, a call to the patient or a doctor/nurse from the rehabilitation health facility is needed to confirm ventilation status on day 28 and their last day of mechanical ventilation.

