4.3 Secondary Outcomes Analysis

For the secondary outcomes outlined in section 2.2.1, a chi-squared test of independence will be used to compare the proportions between groups where appropriate. Odds ratios with 95% confidence intervals, and p values will be reported.

Hospital-free days alive, ICU-free days alive, ventilator-free days and organ support-free days will be respectively analyzed as: the number of days out of hospital alive; the number of days out of ICU alive; the number of ventilator-free days alive (alive and free of invasive mechanical ventilation); and the number of organ support-free days alive (alive and free of invasive mechanical ventilation, non-invasive mechanical ventilation, high flow nasal cannula oxygen and vasopressor therapy) through day 28;

death up to 28 days will be assigned a value of -1. These outcomes will be analyzed using ordinal logistic regression.

The post-treatment D-dimer will be compared by means of linear regression (ANCOVA), adjusted for baseline. Since the D-dimer assay differed across sites, the raw values are not comparable. Therefore, the D-dimer will be analyzed as the logarithm of D-dimer x upper limit of normal (ULN) by taking the natural logarithm of the ratio of the actual d-dimer value divided by the ULN for the assay used.

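### Patients already on qualifying high-flow nasal oxygen can be enrolled, but SAP 4.3 does not adjust the organ support-free days model for it, which costs precision

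*Protocol*

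**What the plan says.** **Entry.** Protocol 4.0, exclusion criterion 14, removes patients on non-invasive or invasive positive pressure ventilation at screening, with the note that "high flow oxygen delivery via nasal cannula is acceptable and is not an exclusion criterion".

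**Outcome.** Protocol Appendix 4: "Organ support is defined as receipt of non-invasive mechanical ventilation, high flow nasal cannula oxygen, invasive mechanical ventilation, or vasopressor therapy". The score is a count: "Defined as the number of days that a patient is alive and free of organ support through 28 days after trial entry". Its counting rule is "Only time before organ support and after the last use of organ support are counted", so free days between two episodes of support are lost. In-hospital death scores -1 in Appendix 4; SAP 4.3 gives -1 to any death up to day 28. SAP 4.3 describes the outcome as days "alive and free of invasive mechanical ventilation, non-invasive mechanical ventilation, high flow nasal cannula oxygen and vasopressor therapy".

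**What counts as high-flow oxygen.** Appendix 4 requires a flow of at least 30 L/min with FiO2 of at least 40%. Appendix 3 uses a different rule: "a patient is considered to be receiving high flow nasal cannula (HFNC) therapy when the flow rates provided by this device are >30 L/min", with no FiO2 limit. SAP 4.3 and exclusion criterion 14 give no threshold.

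**Analysis.** For the four day-count outcomes SAP 4.3 says "These outcomes will be analyzed using ordinal logistic regression" and names no covariate. In the same section, D-dimer is adjusted for its baseline value. Protocol 7.2 adjusts binary and continuous secondary outcomes for age only. Protocol 3.0 stratifies randomization by site and age. The protocol's tertiary objective lists hypoxia as a factor to explore, but SAP 4.4 has no hypoxia or oxygen-support subgroup. No analysis in the SAP therefore uses baseline respiratory support.

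**The concern.** High-flow oxygen is the one respiratory support in the Appendix 4 definition that a patient may be receiving at entry. Someone on it at the qualifying level has no support-free time before the first episode and has lost at least one day before treatment can act. Status at entry is thus likely to be a strong predictor of the score, and neither the stratification nor the model uses it.

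At stake is how informative this outcome will be. Leaving out a strong baseline predictor leaves avoidable between-patient variation in the comparison. It also pulls a proportional-odds estimate toward 1, and nothing corrects for a chance difference between arms in the number who start on support. Because the trial is open-label, an adjustment added only after an imbalance has been seen would carry less weight than one specified now.

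**Working it through.** **1. The plan's own figure.** The documents give no power or sample size for organ support-free days. The only stated figure is 462 for the primary outcome (protocol 7.1: 50% versus 35%, 90% power, two-sided alpha 0.05, two interim analyses).

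- Pooled formula: n per arm = [1.960 × √(2 × 0.425 × 0.575) + 1.282 × √(0.25 + 0.2275)]² / 0.15² = 226.2, so 227 per arm and 454 in total.
- Efficacy looks at 25% and 75% with Hwang-Shih-DeCani spending (gamma not given; -4 assumed) inflate this by 1.017, to 461.8.

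The 462 is reproduced. High-flow oxygen is not a component of the primary composite, so this figure does not bear on the point.

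**2. What the counting rule does.** Number the days 1 to 28, with day 1 the day of randomization.

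- Patient A has no support at entry, is ventilated on days 10 to 14, then is free. Score: 9 + 14 = 23.
- Patient B is on qualifying high-flow oxygen on day 1 only, and otherwise has the same course. Days 2 to 9 fall between two episodes and are not counted. Score: 14.
- Patient C is on qualifying high-flow oxygen on days 1 to 3 and needs no support afterwards. Score: 28 - 3 = 25.

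One baseline day costs B 9 days against A, yet C still scores well.

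**3. Chance imbalance.** The share on high-flow oxygen at entry is not in the documents; 5%, 10% and 20% are assumed. The 95% range for the difference between arms of 231 is ±1.96 × √(2p(1-p)/231).

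| Assumed share p | Patients of 462 | 95% range (points) | Patients per arm |
|---|---|---|---|
| 5% | 23 | ±4.0 | 9 |
| 10% | 46 | ±5.5 | 13 |
| 20% | 92 | ±7.3 | 17 |

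**4. Effect on the planned model.** Proportional-odds simulation, 462 patients, 600 runs per setting. All inputs are assumptions:

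- controls not on high-flow oxygen: 8% die, 22% are spread evenly over scores 0 to 27, and 70% score 28;
- high-flow oxygen at entry lowers the log-odds by 1.5 and rules out 28 (patients who would have scored 28 get 20 to 27 instead);
- the treatment odds ratio given entry status is 1.8 (log 0.59).

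| Share | Type I error, unadjusted / adjusted | Power, unadjusted / adjusted | Mean log odds ratio, unadjusted / adjusted |
|---|---|---|---|
| 5% | 0.050 / 0.060 | 0.76 / 0.81 | 0.53 / 0.59 |
| 10% | 0.040 / 0.040 | 0.71 / 0.81 | 0.49 / 0.58 |
| 20% | 0.050 / 0.047 | 0.62 / 0.80 | 0.42 / 0.55 |

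Monte Carlo error is about ±2 points for type I error and ±4 for power. On the odds ratio scale the unadjusted means correspond to e^0.53 = 1.70, e^0.49 = 1.63 and e^0.42 = 1.52. Type I error stays near 5% either way, so the loss is in power and in the size of the estimate.

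**The case against.** The strongest reply is that nothing is invalid here. Allocation is concealed and 1:1, so entry status is balanced in expectation, and chance imbalance is already covered by the unadjusted test and its confidence interval. A reader might infer that a difference in this outcome would be confounded by who was on high-flow oxygen. The documents do not support that, and the simulated type I error agrees. This part of the objection stands.

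A reader might also infer that such patients have already failed the outcome at entry. That is wrong too: the score is a day count, and days after the last use of support are counted. Nor does every patient admitted on high-flow oxygen count as supported, because Appendix 4 sets a flow and FiO2 threshold.

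A further objection concerns the data. In Table 5, organ support is recorded from the day 1 column with no screening entry, taken from the chart when available. Maximum FiO2 is recorded from screening, but Appendix 3 says FiO2 and flow are independent settings, so FiO2 alone does not identify high-flow oxygen. A plain day-1 flag could pick up support started after randomization, and adjusting for that would be a mistake. This limits how the covariate must be defined; it does not remove the case for one.

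Finally, the outcome is one of many secondary outcomes that protocol 7.2 calls exploratory, and any prognostic factor could be proposed for adjustment. The first part is true and limits the weight of the point. The second is weaker, because this factor is part of the outcome's own definition.

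**Conclusion.** The point holds as a matter of precision. The plan admits patients who may be on qualifying organ support at entry, scores their outcome accordingly, and names no covariate for it. The omission does not bias the test. It lowers power, gives an odds ratio closer to 1 than the one conditional on entry status, and leaves chance imbalance uncorrected.

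The size cannot be fixed from the documents, because the share on high-flow oxygen is not stated. With an assumed 5% to 20%, the simulated power loss runs from about 5 points (0.81 to 0.76) to about 18 points (0.80 to 0.62). These figures rest on the assumed score distribution, baseline effect and treatment effect, and are illustrative.

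The reach is narrow: one exploratory secondary outcome. The primary outcome, the 462 and the stopping rules are unaffected. The change is worth making because it is cheap.

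**What to change.** Before unblinding, state in SAP 4.3 that the ordinal model for organ support-free days is adjusted for age and for high-flow nasal oxygen in use at or before randomization (yes/no). Define the covariate as support in place before randomization, excluding support started later on day 1. Tabulate this status by arm with the baseline characteristics, and report the unadjusted result alongside.

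Reconcile the high-flow definitions in Appendix 3, Appendix 4 and SAP 4.3, so that the covariate and the outcome use the same one.

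**Cost.** A short addition to the SAP and one covariate. The adjusted odds ratio becomes conditional on entry status, a distinction that SAP 4.2 already draws for the primary outcome, which is why both results should be shown. The eCRF is not among the documents and must be checked to confirm that it separates pre-randomization support from later day-1 support. If it does not, the status would have to be retrieved from the chart.
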